Protocol Title

Lung Transplantation in Chronic Hepatitis C Infection with Post Transplant EPCLUSA Treatment: A Pilot Feasibility and Efficacy Study

Purpose of the Study

Primary objectives

- Assess feasibility, safety and efficacy of Epclusa treatment after lung transplant in those with chronic Hepatitis C Virus infection.
- Establish Sustained Virologic Response (SVR)12 rates in HCV-infected lung transplant recipients treated with EPCLUSA. SVR 12 is the absence of detectable hepatitis C virus in the blood after 12 weeks of antiviral therapy. This is the standard outcome in studies evaluating therapies to treat hepatitis C virus.

Secondary Objective

- Evaluate impact of considering donors who are hepatitis C nucleic acid amplification test (NAT) positive in recipients with pre-existing hepatitis C viremia on wait times and post transplant survival.
 - Are wait times shortened by considering HCV NAT positive donors?
 - Do HCV NAT positive donors otherwise meet criteria for lung donation?

Primary endpoints

- Sustained Virologic Response 12 weeks (SVR 12) in those treated with EPCLUSA
- Adverse events resulting in discontinuation of EPCLUSA
- Eligibility for EPCLUSA treatment within 12 months of lung transplant.
 - If subjects do not have adequate renal function or require medications with significant drug interactions with epclusa, they will not be eligible for treatment. Eligibility is an outcome because it is not known if these factors will limit utility of epclusa in this setting due to common complications associated with lung transplantation.

Secondary endpoints

- Serum HCV RNA levels at 12-, 24-, and 48-weeks after initiation of EPCLUSA
- Adverse events requiring temporary interruption in Epclusa therapy
- 90-day and 1-year post transplant patient survival
- 90-day and 1-year post transplant patient survival in recipients of HCV NAT positive donor organ

Exploratory outcomes

- Change in transient elastography score at 48-weeks post Epclusa treatment

- Acute rejection rates
- Primary graft dysfunction scores
- Infections requiring treatment
- Wait times associated with donor HCV status

Background & Significance

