Epclusa is a fixed-dose combination product containing sofosbuvir, an HCV NS5B polymerase inhibitor, and velpatasvir, an HCV NS5A inhibitor. It was approved by the FDA in June 2016 for the treatment of chronic HCV genotypes 1, 2, 3, 4, 5 and 6. The first antiviral approved to treat all major forms of HCV, it can be used in patients with compensated and uncompensated cirrhosis, as well as those without cirrhosis. Response rates, defined as a RCV RNA pcr less than the lower limit of quantification (<LLOQ) 12 weeks after completion of therapy (SVR12), in those without decompensated cirrhosis who were treated for 12 weeks range from 94-99%. It is recommended as first line therapy by the American Association for the Study of Liver Diseases (AASLD) and the Infectious Diseases Society of America (ISDA) for treatment of chronic HCV infection with genotypes 1, 2, 3, 4, 5 and 6.

The goal of this study is to assess whether a strategy of performing lung transplant in individuals with end stage lung disease and chronic HCV infection, and then treating them post-transplant with Epclusa is feasible, safe and effective at curing HCV.

The reason to wait until after lung transplant to treat the hepatitis C virus is two-fold. First, it opens up the donor pool to include those with chronic hepatitis C. This can potentially shorten wait times and increase the number of lungs used for transplantation, which could increase access to a life-saving transplant and for those suffering with end stage lung disease and decrease deaths on the waiting list. The second reason to adopt this strategy is that it allows those with rapidly progressive lung disease to be transplanted prior to completing 12 weeks of antiviral

therapy, during which time their lung disease might progress to the point where they are too sick to survive a lung transplant.

As a first step, this study includes only lung transplant candidates with chronic HCV infection. For these candidates with chronic HCV infection, consideration would be given to organ offers from both HCV NAT positive and HCV NAT negative donors. Donors would be accepted based on quality and suitability, independent of HCV status. *There would be no intentional utilization of an HCV positive donor into an HCV negative recipient.*

Design & Procedures

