Prospective, open-label study evaluating feasibility, safety and efficacy of Epclusa treatment in lung transplant recipients. Lung transplant recipients who are chronically infected with hepatitis C virus will be treated with Epclusa for 12 weeks and evaluated for evidence of hepatitis C virus in their blood at 12, 24 and 48 weeks after therapy initiation.

Individuals with chronic hepatitis C infection will be enrolled prior to transplant. Participation in this study will allow individuals with active chronic hepatitis C infection to be considered for candidacy for lung transplant, as chronic HCV infection has, until this study, been considered a contraindication for lung transplant at Duke.

Once the subject has undergone lung transplant, been discharged from the hospital and clinically stabilized (a process that can take weeks to months, depending on complications associated with this lung transplant), the subject will be referred for treatment screening. A regaining of functional status, increasing independence in activities of daily living, and a lack of significant or poorly controlled acute infections or need for hospitalization are markers of clinical stability which will be determined by the treating transplant pulmonologist.

If eligible, the subject will then be given study drug which will be taken for 12 weeks. Subject will be monitored throughout treatment course for adverse events. Upon completion of therapy, repeat testing will be performed to assess for clearance of the virus from the blood. Subjects will be followed for 48 weeks after initiation of study drug to monitor for recurrence and to evaluate change in degree of liver stiffness, as assessed by transient elastography.

Regimen (drug/dose/frequency)

Epclusa (sofosbuvir 400mg/velpatasvir 100mg) 1 tablet PO or VT daily x 12 weeks, taken with or without food.

Projected duration of treatment

12 weeks

Projected duration of enrollment

2 years

Study Details

- Treating pulmonologist will refer for treatment screening visit when clinically appropriate. Repeat HCV PCR and genotyping will be done prior to start of Epclusa treatment as part of the treatment screen.

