- Drug-drug interaction considerations: Many lung transplant recipients develop atrial fibrillation after lung transplant and may require treatment with amiodarone. Due to risk of bradycardia associated with concomitant use of epclusa and amiodarone, subjects must be off amiodarone for at least 60 days in order to be eligible for epclusa treatment.
- After 5 subjects complete 12 weeks of epclusa treatment, a preplanned analysis will be performed to assess safety and efficacy.
- HCV positive donors will have blood collected at time of procurement to be sent for genotyping and quantitative PCR.
- Because Epclusa is FDA-approved for all HCV genotypes, there is no anticipated safety risk associated with the organ donor having a different genotype than recipient.

Early discontinuation

If a subject decides to withdraw from the study prior to completion, the subject will be asked to return for a final visit for data collection.

Selection of Subjects

Inclusion criteria:

1. HCV RNA $\geq 10^3$ IU/ml at screening
2. Chronic HCV infection, defined as positive HCV antibody and/or HCV RNA more than 6 months prior to screening
3. HCV Genotype 1, 2, 3, 4, 5 or 6
4. Otherwise eligible for lung transplant at study site

Exclusion criteria:

1. Age < 18
2. Treatment with any of the following agents:
 - Amiodarone. Subjects previously treated with amiodarone must have stopped the amiodarone at least 60 days prior to day 1 SOF/VEL
 - Carbamazepine, phenytoin, phenobarbital, oxcarbazepine
 - Rifabutin, rifampin or rifapentine
 - HIV regimens containing tenofovir, tipranavir/ritonavir, or efavirenz
 - St John's wort
 - Modafinil

3. Have any serious or active medical or psychiatric illness which, in the opinion of the investigator, would interfere with subject treatment, assessment or compliance
4. Hepatitis B surface antigen positive (This is checked at the time of transplant evaluation.)
. (
5. History of hepatic encephalopathy or variceal hemorrhage
6. Abnormal hematological and biochemical parameters, including:
 - Hemoglobin <8g/dL
 - Platelets <= 50,000/mm³
 - ALT (alanine aminotransferase), AST (aspartate aminotransferase) or alkaline phosphatase >=10 times ULN
 - Total bilirubin >3mg/dL
 - Severe renal impairment, ie creatinine clearance (CrCl) <30mL/min
7. Pregnant women or women planning to become pregnant
8. Women who are breastfeeding
9. Active or recent history (<=1 year) of drug or alcohol abuse

Subject Recruitment and Compensation

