- Transient Elastography

Schedule of Assessments

Study Week +/- 21 days	Lung transplant evaluation	Study Screening	Transplant	Treatment Screening Visit	Treatment initiation (can be combined with treatment screening)	Week 4	Week 8	Week 12	Week 24	Week 48
Study Informed consent		X								
Inclusion/Exclusio n		X								
Demographics		X								
Medical history				X						
Physical exam	X			X		X	X	X	X	X
Vital Signs Height/Weight	X			X		X	X	X	X	X
Confirm treatment eligibility				X						
Serum HCG				X						
Liver biopsy	X									
Transient elastography	X									X
HCV PCR	X			X				X	X	X
HCV genotype	X			X						
Routine labs (CBC, CMP, Mg, PT/INR)	X			X		X	X	X	X	X
Drug and alcohol Screen	X									
Hepatitis B Screen	X									
EKG	X			X						
Dispense Drug					X (6 week supply)	X (6 week supply)				
Review Con Meds				X		X	X	X	X	X
Review for AEs						X	X	X	X	X
Donor HCV PCR/genotype (if donor HCV NAT positive)			X (At time of procurement)							

*All follow-up visits may occur inpatient or outpatient.

*Boxes marked in red are part of standard of care for lung tx candidates/recipients.

Note: To ensure compliance with CMS guidelines, all studies involving patient care at Duke are required to have study protocol-specific EMR build for ordering, resulting and billing of protocol-related activities. This ensures SOC activities are billed to insurance and protocol-related activities are billed to the study. This is referred to as EPIC initiation. The EPIC build is specific to each protocol and will not be used for any future studies.

References

ⁱ <http://www.cdc.gov/nchs/fastats/copd.htm>

ⁱⁱ <https://www.unos.org/about/annual-report/>

ⁱⁱⁱ Doucette KE¹, Halloran K², Kapasi A², Lien D², Weinkauf JG². Outcomes of Lung Transplantation in Recipients with Hepatitis C Virus Infection. *Am J Transplant.* 2016 Mar 21 [Epub ahead of print].

^{iv} Englum BR¹, Ganapathi AM², Speicher PJ², Gulack BC², Snyder LD³, Duane Davis R², Hartwig MG². Impact of donor and recipient hepatitis C status in lung transplantation. *J Heart Lung Transplant.* 2016 Feb;35(2):228-35

^v J. Levitsky, K. Doucette. **AST Infectious Diseases Community of Practice.** Viral hepatitis in solid organ transplantation. *Am J Transplant*, 13 (Suppl 4) (2013) 147-68.

^{vi} Doucette K¹, Sumner S², Weinkauf J³. **Treatment of hepatitis C in a lung transplant recipient with sofosbuvir and daclatasvir.** *J Heart Lung Transplant.* 2016 Feb 8. pii: S1053-2498(16). [Epub ahead of print].

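### The SVR12 sample is timed from drug start, not from the last dose, so the Week 24 PCR can fall less than 12 weeks after treatment ends

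*Combined protocol and SAP*

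**What the plan says.** Purpose of the Study makes SVR12 among treated subjects a primary endpoint. It also makes adverse events that end Epclusa treatment a primary endpoint, and lists "Adverse events requiring temporary interruption in Epclusa therapy" as a secondary one, so the plan expects both events.

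SVR12 is described in two ways. Background & Significance defines response as HCV RNA below the lower limit of quantification, measured "12 weeks after completion of therapy (SVR12". The objectives in Purpose of the Study speak instead of undetectable virus following 12 weeks of antiviral treatment, which can be read as an end-of-treatment result.

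Design & Procedures says that recipients "will be treated with Epclusa for 12 weeks" and are "evaluated for evidence of hepatitis C virus in their blood at 12, 24 and 48 weeks after therapy initiation". The visit list and the Schedule of Assessments table place HCV PCR at the same three visits, and the table is headed "Study Week +/- 21 days". No PCR is tied to the last dose. Design & Procedures adds: "Subjects will be followed for 48 weeks after initiation of study drug to monitor for recurrence".

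The Early discontinuation section is one sentence. Its condition is "If a subject decides to withdraw from the study prior to completion", and the only step it sets out in that event is that "the subject will be asked to return for a final visit for data collection". It names no HCV PCR, and the schedule has no early-termination column. Data Analysis & Statistical Considerations does not say how a treated subject without an SVR12 result is counted. No section says whether doses missed in an interruption are made up.

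**The concern.** The endpoint is defined by time off drug, while the samples are scheduled by time since drug start. The two agree only when the last dose falls exactly at Week 12 and the visit takes place on its nominal date. If the last dose moves later or the visit comes early, the Week 24 sample precedes the SVR12 time point. A relapse after that sample would be missed and the subject scored as cured.

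Separately, a subject who leaves the study before Week 24 may have no usable result, and the plan leaves open whether that subject is dropped, failed or scored on an earlier sample. In a pilot of 10, either problem in one or two subjects visibly changes the primary efficacy rate.

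**Working it through.** There is no plan figure to reproduce: the 10 subjects are stated without a derivation, and the study is described as not powered for comparisons. The check is of visit timing, then of how sensitive the proportion is to missing results.

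**Inputs from the documents.** Treatment of 12 weeks; PCR at Weeks 12, 24 and 48 from initiation; window of 21 days (3 weeks) either way; 10 enrolled, so at most 10 treated; 94–99% response in the Background section, used only for illustration.

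**Assumptions.** Interruption length d (2 and 4 weeks), with missed doses made up; number without a result m (1 to 3); cure rate q among those without a result (0 to 1).

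**1. Uninterrupted completer.** Gap = visit week − 12. Week 24 gives 12 weeks, with a window range of 9 to 15.

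**2. Interruption of d weeks, doses made up.** The last dose is at Week 12 + d.

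| d | Week 24 gap, 12 − d | Range with window | Week 48 gap, 36 − d | Range with window |
|---|---|---|---|---|
| 2 | 10 | 7 to 13 | 34 | 31 to 37 |
| 4 | 8 | 5 to 11 | 32 | 29 to 35 |

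If doses are not made up, the last dose stays at Week 12 and step 1 applies.

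**3. Drug stopped at week s, subject stays in the study.** Week 24 gap = 24 − s.
- s = 4: 20 weeks (17 to 23).
- s = 8: 16 weeks (13 to 19).
- The nominal gap is at least 12 weeks for any stop up to Week 12. The early window edge, 21 − s, is at least 12 for stops up to week 9.

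**4. Withdrawal from the study.** Before the Week 12 visit, the only scheduled PCRs are pre-treatment, so the result is missing. Between the Week 12 and Week 24 visits, the last scheduled PCR is the Week 12 sample, which for a subject on schedule is at the end of treatment.

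**5. Effect of the counting rule.** Take 10 treated, m without a result and everyone else cured, with exact (Clopper–Pearson) 95% intervals.

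| m | Dropped | Counted as failure |
|---|---|---|
| 1 | 9/9 = 100% (66.4–100) | 9/10 = 90% (55.5–99.7) |
| 2 | 8/8 = 100% (63.1–100) | 8/10 = 80% (44.4–97.5) |
| 3 | 7/7 = 100% (59.0–100) | 7/10 = 70% (34.8–93.3) |

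With n treated, scoring one subject as success rather than failure moves the rate by 1/n, which is at least 10 points for n ≤ 10. Dropping rather than failing a subject makes the same difference only when all observed subjects are cured.

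**6. Direction of bias.** Let p be the cure rate among the observed. With 10 treated, the true rate is [(10 − m)p + mq]/10. Dropping the missing gives a bias of m(p − q)/10; counting them as failures gives −mq/10. For m = 2 and p = 0.94 to 0.99:

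| q | Dropped | Counted as failure |
|---|---|---|
| 0 | +18.8 to +19.8 points | 0 |
| p | 0 | −18.8 to −19.8 points |
| 1 | −1.2 to −0.2 points | −20 points |

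**The case against.** A reader might infer that subjects who stop or interrupt Epclusa never get a valid result. The documents do not support that. The Early discontinuation sentence concerns leaving the study, not stopping the drug. The 48-week follow-up in Design & Procedures has no exception for those who stop, and step 3 shows their nominal Week 24 PCR falling 12 or more weeks after the last dose. Interrupters are affected at Week 24 only if doses are made up (window aside), and they still have a Week 48 PCR. That sample is well past the SVR12 time point and cannot separate late relapse from reinfection, but it does show whether virus has returned.

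A reader might also infer that SVR12 is biased upward overall. Step 6 shows that the direction depends on a counting rule the plan does not state. An endpoint defined among the treated is compatible with an all-treated denominator, under which missing results counted as failures cannot inflate the rate. Nor does a subject who leaves before the Week 12 visit carry a falsely negative on-treatment PCR, because none is scheduled.

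These objections stand, and they narrow the point. They do not answer the timing problem: no rule ties the SVR12 sample to the last dose, and the window alone permits sampling at 9 weeks. That the study is a descriptive pilot limits the consequences, but establishing the SVR12 rate is one of its stated primary objectives.

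**Conclusion.** The concern holds as a timing defect with a missing-result gap attached. As written, the Week 24 PCR can fall 9 weeks after the last dose in an uninterrupted completer. After an interruption with doses made up, it falls at 10 or 8 weeks for 2 or 4 weeks missed, and at 7 or 5 weeks at the early window edge. Reading such a sample as SVR12 can only err upward, on the premise that sampling early may miss a relapse but does not turn a cured subject into a failure.

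A subject who withdraws from the study before Week 24 has no assured result. The size of that gap is 10 points or more per subject between scoring success and failure, with 10 or fewer treated. The numbers interrupted, withdrawn and treated are not known, so no overall bias can be stated. The claims that early stoppers have no valid result, and that the SVR12 rate is necessarily inflated, do not hold.

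**What to change.** - Define the SVR12 sample as the first HCV PCR taken 12 weeks or more after the actual last dose, with a window that does not open before 12 weeks. Shift the Week 24 visit when the last dose moves later, and use Week 48 if no earlier valid sample exists. This works whether or not missed doses are made up, on which no view is taken here.
- Reconcile the SVR12 wording in the objectives with that in Background & Significance.
- Add HCV PCR to the final visit for subjects who withdraw. It counts as SVR12 only if it meets the 12-week condition.
- Report SVR12 with all treated subjects in the denominator, counting those without a valid result as not achieving it, and add an observed-only sensitivity table. The main figure is then conservative, as step 6 shows, and the two tables together show how far it depends on missing results.
- State explicitly that subjects who stop the drug stay in HCV follow-up. This only clarifies what Design & Procedures already implies.

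The cost is mainly protocol wording. HCV RNA at 24 weeks from initiation is a secondary endpoint, so for the few subjects affected either that time point shifts or one extra blood draw is needed. The reported SVR12 rate may be slightly lower.

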Given the promising initial reports, many renal transplant centers are now using HCV positive donors in order to minimize wait times for their HCV positive recipients, and then treating them with DAA regimens post-transplant to clear the HCV infection and preserve liver function. This strategy appears to be both safe and effective based on a single center retrospective review of 43

renal transplant recipients, 19 of whom received organs from HCV antibody positive donors who were treated with 4 different DAA regimens. 100% of the patients in this cohort achieved SVR 12, regardless of DAA regimen used, immunosuppressive induction agent or HCV status of donor. While wait times were significantly shorter in the HCV-positive donor cohort (median 485 days vs 969 days), there was no difference in allograft function or patient survival post-transplant.^{ix}

Lung transplant recipients require the highest levels of maintenance immunosuppression for solid organ transplant; therefore, establishing efficacy in this population is critical for the solid organ transplant community as a whole. It is also an important and necessary step in working towards more widespread use of HCV positive donors. Again, this is particularly relevant in lung transplantation as lungs remain the least likely of the commonly transplanted organs to be utilized with only 17% of multi-organ donors providing lungs. HCV positive donors are routinely turned down due to published reports describing notably worse survival and major liver complications in HCV negative recipients receiving lungs from HCV positive donors,^x however the potential to treat and make these lungs useful could revolutionize solid organ transplant and save thousands of lives.

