10 subjects will be enrolled. Subjects will be identified during the transplant evaluation phase by the clinical team. The clinical team will assess subject's willingness to participate in the study prior to being approached by the research team. Due to active chronic HCV infection currently being considered a contraindication to transplant at Duke, declining to enroll in the study may impact the subject's candidacy for transplant. The suitability for transplant is ultimately made by the Lung Transplant Team, and dependent on multiple factors. Agreeing to participate in this study is not a guarantee for transplant. Subjects will not be compensated for participating in this study; however, subjects will receive study drug free of charge.

Consent Process – see Section 14 of the e-IRB submission form.

Risk/Benefit Assessment

The most common adverse reactions observed with treatment with EPCLUSa for 12 weeks are headache and fatigue. Bradycardia can occur when taken with amiodarone.

Hepatitis B virus reactivation: There have been case reports of hepatitis B reactivation with Epclusa treatment. All subjects will be screened for hepatitis B prior to enrollment.

Costs to the Subject

There will no additional costs to the subjects as a result of participating in this study. Every attempt will be made to coordinate study visits with routine clinical care.

Data Analysis & Statistical Considerations

This study is a small, pilot feasibility study and therefore not powered for comparative statistics. Descriptive and non-parametric statistics will be performed. A matched, case-control cohort will be based on age and underlying lung disease from same center over same time period will be used to evaluate survival outcomes. An unadjusted Kaplan-Meier survival analysis for cumulative survival will be performed.

Data & Safety Monitoring

In accordance with federal regulations the PI will monitor for, review, and promptly report to the IRB, appropriate institutional officials, sponsor, coordinating center and the appropriate regulatory agency head all unanticipated problems involving risks to subjects or others that occur in the course of a subject's participation in a research, all AE reports will be reported per the DUHS IRB policies.

Data collection, storage and confidentiality

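### Hepatitis B reactivation is a named Epclusa risk, yet the only scheduled hepatitis B test is at transplant evaluation and is not repeated before post-transplant dosing

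*Combined protocol and SAP*

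**What the plan says.** The Risk/Benefit Assessment states the hazard and the answer to it together: "There have been case reports of hepatitis B reactivation with Epclusa treatment. All subjects will be screened for hepatitis B prior to enrollment". Exclusion criterion 4 under Selection of Subjects gives the marker and the timing: "Hepatitis B surface antigen positive (This is checked at the time of transplant evaluation". In the Schedule of Assessments table, the row "Hepatitis B Screen" has a single mark, in the transplant evaluation column. The content of that screen is not defined further, and no post-transplant visit list contains a hepatitis B test.

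Several steps separate that test from the first dose. The subject waits for an organ, is transplanted, and is then discharged and stabilised, "a process that can take weeks to months, depending on complications associated with this lung transplant" (Design & Procedures). On the drug burden after transplant, Background & Significance says: "Lung transplant recipients require the highest levels of maintenance immunosuppression for solid organ transplant".

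Other checks are made close to dosing. Study Details and the table repeat HCV PCR and genotype at treatment screening. An EKG is repeated there, serum HCG is done where relevant, and the table has a row for confirming treatment eligibility. Treatment Initiation allows screening and the start of drug to be a single visit.

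**The concern.** The hazard arises when the drug is taken, but the only check is tied to study entry. If a subject's hepatitis B status changed without symptoms after evaluation, the plan followed exactly would still dose that subject on the old result. Recognition and treatment of hepatitis B could then come late, in someone who is immunosuppressed and also has hepatitis C.

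The plan treats its other named drug hazard differently. Bradycardia with amiodarone is handled by a washout of at least 60 days counted back from day 1 of study drug. Hepatitis B has no comparable rule at dosing.

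**Working it through.** No formula in the plan bears on this point. The check is a count from the Schedule of Assessments table and the visit lists, then a reading of what each safeguard could detect.

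**1. Tests by visit**

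| Test | Transplant evaluation | Treatment screening | Wk 4 | Wk 8 | Wk 12 | Wk 24 | Wk 48 |
|---|---|---|---|---|---|---|---|
| Hepatitis B screen | X | – | – | – | – | – | – |
| Routine labs, including CMP | X | X | X | X | X | X | X |
| HCV PCR | X | X | – | – | X | X | X |
| HCV genotype | X | X | – | – | – | – | – |
| EKG | X | X | – | – | – | – | – |

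Post-transplant draws = 1 (treatment screening) + 5 (weeks 4, 8, 12, 24, 48) = 6. Hepatitis B tests on those draws = 0.

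**2. Age of the result at day 1**

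Age = time from evaluation to transplant + time from transplant to first dose. The documents set no limit on the first term. The second is described only as weeks to months, and the related primary endpoint is framed as "Eligibility for EPCLUSA treatment within 12 months of lung transplant". No maximum age for the result follows from the plan.

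**3. Whether the eligibility check at treatment screening closes the gap**

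Exclusion 4 fixes its test at transplant evaluation and no new one is scheduled, so re-applying it would reuse the old result. The reasons the Primary endpoints section gives for post-transplant ineligibility do not include hepatitis B: "If subjects do not have adequate renal function or require medications with significant drug interactions with epclusa, they will not be eligible for treatment". The clinical stability standard, under which "a lack of significant or poorly controlled acute infections or need for hospitalization are markers of clinical stability", may hold back a visibly ill subject, but it would not show a silent change.

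**4. Where a hepatitis B flare could be taken for hepatitis C**

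Of the 5 draws after the start of drug, 3 carry an HCV PCR (weeks 12, 24 and 48), leaving 5 − 3 = 2 without one (weeks 4 and 8). An enzyme rise with undetectable HCV RNA points away from hepatitis C. Background & Significance gives response rates of 94–99% for 12 weeks of treatment without decompensated cirrhosis, so hepatitis C would not usually explain a rise at week 24 or 48. The confusion is therefore mainly at weeks 4 and 8. Week 4 is also when the second supply is dispensed: 6 + 6 = 12 weeks, so no later dispensing visit acts as a checkpoint.

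**5. Cost in assays**

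Let n be the subjects reaching treatment screening and k those with either marker positive (0 to n; no prevalence is given). Two markers each, plus HBV DNA for positives, gives 2n + k.

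- n = 10: 20 + 0 = 20, up to 20 + 10 = 30.
- n = 5 (assumed, since enrolment does not guarantee transplant): 10 + 0 = 10, up to 10 + 5 = 15.

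The total is lower if core antibody is already in the existing screen.

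**The case against.** The strongest case against is that subjects are already watched closely. A CMP is drawn at every post-transplant study visit, and adverse events are reviewed at every visit after the start of drug. Treatment screening includes an examination, a history review and collection of transplant and donor chart data. Exclusion 3 gives the investigator discretion, and a safety analysis follows the first 5 completers. The protocol speaks only of case reports, and surface-antigen-positive subjects are already excluded. The sentence on immunosuppression is an argument about hepatitis C efficacy, not about hepatitis B. The screen may already contain core antibody, and clinicians may repeat it as routine care.

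Most of this stands, and it limits the size of the point. It does not answer it, because none of these safeguards tests for hepatitis B and the protocol requires no repeat.

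A reader might infer that exclusion 6 lets dosing proceed until ALT or AST reaches 10 times ULN. The text does not support that: the list of abnormal values is introduced as examples, so it is open. A reader might also infer that hepatitis C would hide a flare throughout follow-up. The HCV PCR at weeks 12, 24 and 48 argues against that.

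The objection also carries a warning about the remedy. Withholding Epclusa from a transplanted, immunosuppressed subject with HCV viremia has its own risk; Background & Significance cites worsening fibrosis in such recipients. A rule that stopped drug automatically could harm the person it is meant to protect.

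**Conclusion.** The point holds as a subject-safety gap: one hepatitis B test before transplant, none in the 6 post-transplant draws, and no stated limit on the age of the result at dosing. The count is firm. The consequence is less certain. It assumes that hepatitis B status can change or become active between evaluation and dosing, and the documents give no rate for this. The number affected is unknown and could be 0 of 10.

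Two further readings should be resisted. The primary endpoint of adverse events leading to discontinuation is not biased, because its count does not depend on whether an event is attributed to hepatitis B or C. Nor do the Risk/Benefit Assessment and exclusion 4 contradict each other; both place the test before enrolment, and the issue is that it is not repeated. The point also does not establish that the existing screen is surface antigen alone, only that no other marker is named.

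Because the change is cheap and uses a draw already planned, it should be made.

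**What to change.** 1. State what the existing hepatitis B screen contains. Add surface antigen to the treatment screening draw, with core antibody if the screen does not already include it, and HBV DNA if either is positive.
2. Require the result to be reviewed before drug is dispensed. Where screening and initiation are to be combined, draw the test at an earlier routine visit.
3. Let a new positive result prompt hepatology review and a recorded decision between managing hepatitis B alongside Epclusa and deferring treatment. Say how a deferred subject counts in the 12-month eligibility endpoint.
4. As a secondary measure, add a hepatitis B test when ALT or AST rises on treatment, particularly at weeks 4 and 8. The investigators should choose the threshold; the documents offer none for this use.

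Exclusion 4, the Risk/Benefit Assessment, the Treatment Screening Visit list and the table need matching edits, and the protocol-specific EMR build needs an update. The cost is about 2 to 3 assays per subject reaching treatment screening. Tests triggered under item 4 are extra and cannot be counted in advance. The main practical downside is a possible short delay in starting therapy.
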